- Diagnosis of MTC could be as early as 1995-2000. The centers will search their databases for the prevalent MTC patients and review the records to consider recruitment using 2010 as a cutoff, without any limitation for the date of diagnosis. The prescription frequency of vandetanib or any other treatment for MTC should be reported. All efforts will be made to report safety assessments according to specifications in the SmPC, based on the data that will be available in the patient charts (see [Appendix B](#)).

Data collection and reporting will be performed until objective progression, or until the end of study (whichever occurs first). For all patients end of study is defined as 14 months after the last prospective patient has been enrolled in the study and when at least 10 events in each treatment group have been observed. If all patients have progressed prior to 14 months after the last patient is recruited, the study will stop.

The minimum follow-up time period of 14 months for prospective arm (not retrospective) is appropriate because approximately 80% of patients who had an objective response in a pivotal Phase III study achieved their response within 14 months of starting vandetanib (3).

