#### 4.3 EXCLUSION CRITERIA

- E 01. Current or planned inclusion/participation in a clinical trial, not applicable for retrospective patients.
- E 02. Patients already receiving vandetanib or who have received vandetanib for their MTC before the study first visit, not applicable for retrospective patients.
- E 03. Contraindications according to the vandetanib SmPC, not applicable for retrospective patients and for patients who do not receive vandetanib:
- A) Patients with a QTc interval over 480 msec:
    - Congenital long QT syndrome
    - Concomitant use of vandetanib with the following medicinal products known to also prolong the QT interval and/or induce Torsades de pointes: Arsenic, cisapride, erythromycin intravenous, toremifene, mizolastine, moxifloxacin, Class IA and III antiarrhythmics
  - A) Currently pregnant or breast-feeding, not applicable for retrospective patients.
  - B) Hypersensitivity to the active substance or to any of the excipients, not applicable for patients who do not receive vandetanib.
  - C) Severe renal impairment: creatinine clearance <30 mL/minute calculated by Cockcroft-Gault formula, not applicable for patients who do not receive vandetanib (See [Appendix D](#)).
  - D) Serum bilirubin greater than  $1.5 \times$  the upper limit of reference range (ULRR), not applicable for patients who do not receive vandetanib.
  - E) Potassium, magnesium or calcium outside the normal laboratory range, not applicable for patients who do not receive vandetanib.

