## **5 WITHDRAWAL OF PATIENTS**

### **5.1 CRITERIA FOR WITHDRAWAL**

Patients may be withdrawn from the NIS at any time. Specific reasons for withdrawing a patient from this NIS are:

1. Voluntary withdrawal by the patient who is at any time free to withdraw his/her participation in the NIS, without prejudice to further treatment (not applicable for retrospective patients).
2. Incorrect enrollment (inclusion/exclusion criteria are not fulfilled).
3. Inclusion in a clinical trial at any time during the study (not applicable for retrospective patients).

Discontinuation of the patient treatment is not a criterion for withdrawal from the study. In this case, the patient can continue in the study, until death, loss to follow-up, or end of study.

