### **5.2 PROCEDURES FOR WITHDRAWAL**

For prospective patients: patients who withdraw should be asked about the reason(s) for their withdrawal. No specific procedures after withdrawal are required per study but continuation of patient assessment and treatment according to routine clinical practice.

No further data will be collected on prospective patients following withdrawal from the study.

Prospective patients who were not included (eg, for restrictive inclusion/exclusion criteria) or withdrawn from the study (eg, withdrawn due to AE but continuation of assessment and treatment according to routine practice) will still be considered for the retrospective data collection: if they meet the inclusion criteria for the retrospective data collection, the same patient ID will be used in the study database and the patient will be classified as retrospective patient for data analyses.

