## 7 STUDY CONDUCT

### 7.1 PATIENT ENROLLMENT

For prospective patients, once vandetanib is launched in the country and the participant site has the appropriate local approvals, the Investigator will systematically identify and invite to participate in the study every patient who fulfills all the study inclusion criteria and none of the exclusion criteria.

The Principal Investigator will:

1. Obtain signed informed consent from the potential patient (except for retrospective patients).
2. Perform the RET determination in those patients where it is needed to confirm eligibility for prospective patients, provided that a biopsy sample is available and provided that no intervention is needed that would not have been done otherwise to obtain this sample. Verify the RET mutation negative status for retrospective patients.
3. Register the patient in the Web-based Data Capture (WBDC) system when the patient is entered into screening and/or is enrolled.

The recruitment of patients will be centrally controlled by the study team through the WBDC system. Therefore, in order to achieve the appropriate study sample target, it is of great importance that the Investigator registers in the study WBDC system, **immediately after known**, the information related to eligibility of the patient, even if some of these information are incomplete in the beginning.

All the prospective patients who sign the consent form will be allocated an E-code by the WBDC system. For patients who enter into screening period, but are not finally eligible, they will be registered in the WBDC as screening failure and withdrawn. All the screened patients will be registered in the site screening log and reason for withdrawal documented.

Applicable for retrospective patients: the site will search the databases for the prevalent MTC patients and review the records to consider recruitment using 2010 as a cutoff without any limitation for the date of diagnosis and identify among these patients all those who were RET mutation negative, all of whom should be included into the study (unless if there is a contract with another company for a clinical trial that precludes this).

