### **9.3.3 Deaths**

All deaths (both cancer-related and other) that occur during the study up to 60 days after the last dose received must be reported as a SAE. In the event of death, the patient will be considered as having completed the study.

All dead patients will be considered for the retrospective data collection, with no exception.

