#### **Monitoring activities for:**

A qualified and trained Sponsor representative or delegate should perform the following tasks:

- Must ensure that the screening is performed properly and thoroughly, so that no patient who may be eligible is missed from the systematic screening process.
- Must ensure that the patient ICFs are properly signed, dated and stored at the site, for prospective patients.

- SDV:
  - Screening log must be checked thoroughly against the information from any sources of data available at the site, including admission logs, discharge logs, hospital databases, laboratory databases, etc.
  - Patient ICFs must be checked with the information in medical records to ensure the existence of the patients.
  - Some specific study data considered critical for study results validity (eg, RET result, safety data), will be verified against the information in the medical record.
- Ensure that at the study site the NIS documents are archived in accordance with the NIS Investigator's Study File Index by the Investigator.

The extent and nature of monitoring will be decided during the study planning based on design, complexity, number of patients, number of sites, etc., and is detailed in the study source data verification and monitoring plan provided by the coordinating country.

Different signals (eg, low enrollment rate, high rejection rate in a site, continuous lack of availability, repetitive inconsistent answers in the eCRF) should be used as potential identification of low protocol compliance by Investigators, or any other reason for this. If these or any other signal occurs or if the local coordinator is suspicious of a potential non-optimal level of protocol compliance by the site Investigator, especially with respect to the Non-Interventional nature of this study, specific measures should be adopted to evaluate the situation, identify the issue, and implement specific action plans to correct the situation. All NIS documents must be archived by the site for 15 years after last data collected except if local or regional legislation requires longer archiving time. Before final archiving the local MC representative or delegate must ensure all applicable documents are properly filed at the MC and at the study sites.

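### Section 7.1 lets another company's trial contract remove a whole RET-negative retrospective patient, with no rule to keep vandetanib data recorded before that trial

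*Protocol*

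**What the plan says.** Section 7.1 asks each site to search its records for prevalent MTC patients, identify those who are RET mutation negative, and take every one of them: "all of whom should be included into the study (unless if there is a contract with another company for a clinical trial that precludes this"). The exception is attached to the patient. It does not say whether the other trial came before or after vandetanib, or what happens to data recorded before it.

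Elsewhere the protocol treats trial participation as no obstacle for this cohort, and asks for full capture:

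- Section 4.3, E 01: "Current or planned inclusion/participation in a clinical trial, not applicable for retrospective patients".
- Section 5.1, criterion 3: "Inclusion in a clinical trial at any time during the study (not applicable for retrospective patients").
- Section 5.2: prospective patients who were not included or were withdrawn "will still be considered for the retrospective data collection", if they meet its inclusion criteria.
- Section 9.3.3: "All dead patients will be considered for the retrospective data collection, with no exception".
- Section 11.1: monitors are to see that screening is thorough, "so that no patient who may be eligible is missed from the systematic screening process".

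For retrospective patients, section 3.1 sets the data window: "Data collection and reporting will be performed until objective progression, or until the end of study (whichever occurs first").

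**The concern.** A retrospective cohort supports a response rate only if entry does not depend on the outcome. Under section 7.1 a patient can take vandetanib, have a best response and a progression date in the chart, then enter another company's trial and be left out entirely. Selection then takes place after the outcome is known.

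The prospective cohort is handled differently. E 01 and E 02 apply at entry, before any vandetanib. A prospective patient who later joins a trial is withdrawn, and section 5.2 stops further collection without saying that earlier data are discarded. Two patients with the same history can thus be kept in one cohort and lost from the other. Section 13.3 relies on the selection criteria to make the groups comparable enough to pool.

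The exception touches only the RET-negative side, because retrospective entry is open to RET-negative patients only. That is the group for which the amendment was written: 8 RET-negative patients had been enrolled by 2 August 2018, no prospective patient was included after 30 June 2017, and the target is 20 to 25. About 12 to 17 would have to come from elsewhere, mainly from retrospective cases.

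**Working it through.** **1. Are the lost data needed?** ORR, DCR and PFS require nothing after objective progression, and section 3.1 stops retrospective collection there. Sections 6.1 and 7.2 let follow-up run longer, but these endpoints do not use it. For a patient who entered another trial after progressing on vandetanib, all the data needed for these endpoints predate that trial.

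**2. Which way could the loss act?**

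- *Trial after vandetanib.* The SmPC in Appendix B (section 4.2, Duration) allows treatment until the disease progresses or the balance of benefit and risk turns unfavourable. Later trial entrants are therefore plausibly enriched for progression or intolerance. Losing them would tend to lengthen PFS. For ORR the direction is open: a patient who responded, later progressed and then entered a trial is still a responder.
- *Trial before vandetanib.* No clear direction.
- *Never treated with vandetanib.* These patients fall under objective D of section 2 and do not enter the vandetanib ORR.

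**3. The plan's own figure.** Table 1 uses ORR 35% and SD 0.4770, where √(0.35 × 0.65) = 0.47697. The interval is 0.35 ± 1.96 × 0.4770/√n:

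- n = 20: half-width 20.9 points, 14.1% to 55.9%
- n = 25: half-width 18.7 points, 16.3% to 53.7%
- n = 30: half-width 17.1 points, 17.9% to 52.1%

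All three rows match Table 1. They are not in dispute and serve only as a scale.

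**4. Illustrative shift in ORR.** Let p = 0.35, and let eN and eR be the shares of retrospective non-responders and responders lost. The protocol gives neither, so both are assumptions. Expected ORR among retained retrospective patients:

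q = p(1 − eR) / [p(1 − eR) + (1 − p)(1 − eN)]

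With eR = 0:

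- eN = 10%: 0.35/(0.35 + 0.585) = 37.4%
- eN = 20%: 0.35/(0.35 + 0.520) = 40.2%
- eN = 30%: 0.35/(0.35 + 0.455) = 43.5%

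Pooled with the 8 prospective patients, taken as unaffected: (8 × 0.35 + (N − 8) × q)/N.

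| eN | N = 20 | N = 25 |
|---|---|---|
| 10% | 36.5% | 36.7% |
| 20% | 38.1% | 38.6% |
| 30% | 40.1% | 40.8% |

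Other assumptions, among retrospective patients:

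- eN = eR = 20%: 35.0%, no shift.
- eN = 10%, eR = 20%: 0.28/(0.28 + 0.585) = 32.4%, a fall.

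**5. The same in counts.** Take 7 responders in 20 (35.0%) and drop three patients:

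- all three non-responders: 7/17 = 41.2%
- two non-responders and one responder: 6/17 = 35.3%
- all three responders: 4/17 = 23.5%

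Sign and size depend wholly on who is lost, which the plan does not require anyone to report.

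**The case against.** The strongest reply is that section 7.1 only acknowledges a legal limit. Participation in a trial excludes nobody; only a contract that forbids inclusion does. E 01 sets eligibility, and section 7.1 concedes what the protocol cannot override. A reader might infer that section 7.1 reverses E 01, and the text does not support that. Nor does it breach the monitoring duty in section 11.1, since a patient who was screened and then found barred was not missed. All this stands. What remains is that the limit is drawn around the patient and not around the other company's data.

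It can also be said that a contract which leaves the earlier chart data free does not preclude inclusion, so that section 7.1 would already take the patient and section 6.1 would report the chart. That reading is possible, but the text does not state it, and a site could as easily drop the patient.

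Three further points carry weight. Section 7.1 already sends all screened patients to a site log with a reason, although that sentence follows text about prospective patients. Results are to be shown by cohort as well as pooled, so an unusual retrospective ORR would be visible, though its cause would not. The ORR analysis is descriptive, so no test is affected.

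**Conclusion.** The point holds as a selection rule that can drop patients after their outcome is known, in one cohort and one RET group only, and that is wider than a contract limit needs to be. Upward bias is plausible for PFS. For ORR and DCR it is possible, with unproven direction.

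A reader might infer that the clause inflates the RET-negative ORR by removing vandetanib failures. The documents do not establish this: nothing in them describes the trial entrants, and progression after a response does not make a patient a non-responder.

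The size is unknown. The range of 36.5% to 40.8% against 35% assumes that 10% to 30% of retrospective non-responders and no responders are lost, that 8 prospective patients are unaffected, and that the total is 20 to 25. Adding reclassified patients from Study D4200C00058 to the pool would dilute it. The shift of 1.5 to 5.8 points is well inside the Table 1 half-widths of 18.7 to 20.9 points, but those reflect sampling error only, and a larger sample would not remove a selection effect.

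**What to change.** Replace the parenthesis in section 7.1 with a rule on these lines: *The exception covers only data generated in the other company's trial. A patient who entered that trial after starting vandetanib is included with chart data up to the first treatment in it, and is censored there if not progressed. A patient is left out only if the contract also bars the earlier data.*

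Then:

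- report the number of precluded vandetanib-treated patients from the screening log, with further details only where the contract permits;
- add a bounding RET-negative ORR and DCR that counts them first as non-responders and then as responders. For example, 7 responders among 17 analysed with 3 precluded gives 7/20 = 35.0% to 10/20 = 50.0%.

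The cost is a short rewording, one log field and two sensitivity rows. Sites must check what each contract covers, and a few more charts are abstracted. Real contract bars are still respected.

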## **7.2 PATIENT FOLLOW-UP**

Once the patient is enrolled in the study, every time he/she attends the office/clinic/hospital for routine visits (see follow-up visits description in [Section 3.1](#)), the Investigator will create a visit in the eCRF and record all the available information required for study purposes, together with the dates of these routine visits. Follow-up (labelled as “time points” for retrospective patients) of each patient and collection of data for the study will cease at the death of the patient, loss to follow-up, or at the end of study (whichever occurs first). For safety data collection period, please refer to [Section 9.2](#). For special warnings and precautions for use of vandetanib during the follow-up period (eg, QTc prolongation), please refer to SmPC ([Appendix B](#)).

## **7.3 RESTRICTIONS DURING THE STUDY**

There are no specific restrictions in this study.

## 8 MEASUREMENTS OF STUDY VARIABLES AND DEFINITIONS OF OUTCOME VARIABLES

### 8.1 BENEFIT/RISK

- ORR (using RECIST 1.1)
- DCR (using RECIST 1.1)
- PFS derived (using RECIST 1.1)
- Duration of response and time to response
- Safety:

All efforts will be made to collect the following safety data, for prospective (RET mutation positive or negative) and retrospective RET mutation negative patients:

- AE: All AEs, (for patients treated with vandetanib) will be collected actively throughout the study, and retrospectively for retrospective RET mutation negative patients
- ECGs: QTc prolongation
- Vital signs: blood pressure, heart rate
- Laboratory data:
  - Electrolyte: serum potassium, calcium and magnesium
  - Thyroid stimulating hormone (TSH) at baseline
  - Renal function: creatinine clearance value (Cockcroft Gault formula)
  - Hepatic function: serum bilirubin, aspartate aminotransferase (AST), alanine aminotransferase (ALT), gamma-glutamyltransferase (GGT), alkaline phosphatase (ALP), and albumin.

### 8.2 PATIENTS CHARACTERISTICS

#### *Patient demographics and medical history*

- Age
- Sex
- Co-morbidities
- Chronic drug therapy related to relevant medical conditions at baseline

#### *Disease characteristics*

- First diagnosis of sporadic MTC date
- Date of diagnosis of sporadic, unresectable, locally advanced/metastatic MTC
- Investigator's assessment of symptomatic and aggressive (clinical deterioration, calcitonin [CTN], carcinoembryonic antigen [CEA] doubling time, change of tumor volume, other)

- Date of last determination of disease progression
- RET determination (if more than 1 determination has been done, information from all will be collected):
  - Date of RET assay
  - Mutational status
  - Assay type
  - Tissue type used for assay
  - Date of tissue biopsy
  - Exons analyzed
- Disease assessment (including number/sites of disease locations): at baseline (for all patients and before treatment with vandetanib for the patients who received vandetanib) and at follow-up visits for prospective patients or at any time point for retrospective patients (whenever performed)
- Date of measurements
- Symptoms at baseline (before treatment with vandetanib for the patients who received vandetanib) and at every disease assessment time point (lump at the base of the neck, dysphagia, respiratory difficulty, hoarseness, diarrhea, weight loss, lethargy, asthenia, anorexia and bone pain)
- CTN and CEA doubling time at baseline
- CTN and CEA at every disease assessment time point

***Death/Lost to follow-up***

- Date and cause

***Treatment information:***

- Previous treatments received for the sporadic MTC (including non-pharmacologic)
- For prospective (RET mutation negative and positive status) patients prescribed vandetanib at entry: current and any subsequent treatments for symptomatic, aggressive, sporadic, unresectable, locally advanced/metastatic MTC: date of treatment start and stop (if available)
- For retrospective (RET mutation negative status) patients diagnosed with MTC, and prescribed vandetanib at any time or never prescribed vandetanib: previous, current and any further treatments for symptomatic, aggressive, sporadic, unresectable, locally advanced/metastatic MTC: dates of treatments start and stop (if available)
- For RET mutation negative patients not treated with vandetanib at entry: previous, current and further treatments for symptomatic, aggressive, sporadic, unresectable, locally advanced/metastatic MTC: dates of start and stop (if available)
- Dose adjustments/discontinuations during follow-up (dates of adjustments and doses)
- Opioid use: Dates, doses and routes by generic name

The above information, the monitoring of which is specifically recommended in the SmPC, will be collected during the study visits/reporting time points when available in medical records.

## 9 SAFETY REPORTING

The Principal Investigator is responsible for ensuring that all staff involved in the study is familiar with the content of this section.

### 9.1 DEFINITIONS

#### 9.1.1 Definition of AE

An AE is the development of an undesirable medical condition or the deterioration of a pre-existing medical condition following or during exposure to a pharmaceutical product, whether or not considered causally related to the product. An undesirable medical condition can be symptoms (eg, nausea, chest pain), signs (eg, tachycardia, enlarged liver) or the abnormal results of an investigation (eg, laboratory findings, electrocardiogram). In clinical studies, an AE can include an undesirable medical condition occurring at any time, including run-in or washout periods, even if no study treatment has been administered.

The term adverse event is used generally to include any AE whether serious or non-serious.

Refer to [Section 9.2.1](#) for further details of the study safety reporting requirements.

#### 9.1.2 Definition of SAE

A SAE is an AE occurring during any study phase and fulfills 1 or more of the following criteria:

- results in death
- is immediately life-threatening
- requires in-patient hospitalization or prolongation of existing hospitalization
- results in persistent or significant disability or incapacity
- is a congenital abnormality or birth defect
- is an important medical event that may jeopardize the ~~subject~~-patient or may require medical intervention to prevent one of the outcomes listed above

For further guidance on the definition of a SAE, see [Appendix E](#).

